3.2. STUDY OUTCOME MEASURES

3.3. PRIMARY OUTCOME MEASURES

We hypothesize that migraine patients will have a reduction in thalamic μ OR BP_{ND} at the baseline level (see preliminary data). The activation of μ OR neurotransmission, calculated as reduction in μ OR BP_{ND} during a sustained thermal pain threshold stress challenge will also be lower than in controls, and that both these measures will be associated with clinical and experimental pain ratings.

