Subsequently, dynamic image data for each of the receptor scans are transformed on a voxel-by-voxel basis into three sets of parametric maps, which are co-registered to each other. These are (1) a tracer transport measure (K1 ratio, proportional to cerebral blood flow; tracer transport=blood flow x tracer extraction) and receptor-related measures (non-displaceable binding potential, BP_{ND}), encompassing data from (2) 10-40 min (baselines) and (3) 45-90 post tracer administration (pain or control). These parametric images are calculated using a modified Logan graphical analysis (Logan et al., 1996) with the occipital cortex (a region devoid of μ -opioid receptors) as the reference region. The Logan plot becomes linear well within 10min after the start of radiotracer administrations with a slope proportional to the Bmax/Kd + 1 for this receptor site. Bmax/Kd is the "receptor related" measure BP_{ND}.

Blood Collection: Each subject who has agreed to participate in the genetic analysis will have the blood drawn from their arm vein during the PET session(s). Blood will be collected from an intravenous line placed in the arm opposite that used for radiotracer administration.

The blood for the genetic analysis will be collected during each subject's PET scan(s) if they have indicated their interest in participating in the genetic analysis portion of the study. At the beginning of the PET scan(s), blood will be drawn for genetic and biomarker analysis (24 mL maximum). During the PET scan(s) ~6mL of blood will be drawn at twenty minute intervals starting at time 0 minutes. The total volume of blood per PET scan will not exceed 70 mL.

MRI Acquisition: While healthy controls will only undergo one 45min MRI scan, episodic migraine patients will undergo two identical 45min MRI sessions, the week before and the week following the 10 daily HD-tDCS sessions. Before and after the MRI scan(s) participants will complete the PANAS questionnaire.

MRI scans are acquired on a 3 T scanner (General Electric, Milwaukee, WI). These images provide anatomical information for structure identification and will be utilized for the anatomical standardization to the ICBM/MNI atlas coordinate system. This will establish the linear and non-linear warping transformation matrices to be applied to the co-registered receptor binding maps. The acquisition sequence is axial T1 FAST SPGR

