We then compared the migraineurs in the interictal phase with age and gender matched healthy controls. In our preliminary data we noticed lower μ OR BP_{ND} in pain-related brain regions, especially the thalamus (Figure 14), at baseline (no stimulus) (Aim1.1) and during thermal stimulation (STPTS) (Aim1.2). These results indicate that there is higher endogenous μ -opioid neurotransmission interacting with μ OR in migraineurs, even during the interictal phase, either by the higher occupancy or loss of μ -opioid receptors available.

Analysis: First, we will continue to examine differences in baseline µOR BP_{ND} and in the activation of µ-opioid neurotransmission in a large control sample of migraine patients to confirm our preliminary results. A mixed model of variance will be employed, accounting for age and other nuisance or potentially influencing variables (e.g., plasma levels of estradiol, proximity of attacks). Reductions in baseline µOR BP_{ND} and in the activation of u-opioid neurotransmission in migraine compared to controls should be expected. Second, we will investigate individual associations between baseline uOR BP_{ND} levels and their change during the STPTS challenge in the thalamus, other pain-related regions, and acute and chronic pain measures, as well as between µOR BP_{ND} levels and pain frequency by means of pair-wise correlation coefficients. We intend to use either Pearson's version or the Spearman's rank version of the correlation coefficient depending on whether the variables investigated follow normal distribution or not. Subsequently, we shall investigate the joint effect of pain intensity and frequency on the μORBP_{ND} by means of a multiple linear regression analysis where μOR BP_{ND} is the outcome, and the other two are used as predictor clinical variables. The linear regression analysis allows us to identify the effect of either one on µOR BP_{ND} for a fixed level of the other predictor.

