hypothesis was wrong, and only modulation of the pain-related neural networks will be seen in migraineurs (Aim3); however, this is unlikely based on previous successful experience with M1-tDCS and chronic migraine (DaSilva et al., 2011c), and experimental trigeminal pain (DosSantos et al., 2014b). A recent meta-analysis study in non-invasive M1 stimulation for chronic pain indicated an effective size of -0.86 (95% C.I., -1.54, -0.19) on the VAS (Zaghi et al., 2011). Another issue is the accuracy on targeting M1 in our montage. It is important to note that current can concentrate at distinct gyri/sulci sites so current flow, and thus brain activation, is not homogenous across an area of stimulation (Datta et al., 2009). Still, when external landmarks are used to target brain regions with HD-tDCS, computational models improve accuracy, but they are prediction models. In order to address this issue we will confirm the M1 location by using transcranial magnetic stimulation (Zaghi et al., 2010).

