11.2. SAMPLE SIZE CONSIDERATIONS

Taking into consideration a possible 20% dropout during the study, our sample size of 30 patients per group is a conservative number. For comparing two groups in Aim1 and Aim2, a sample size of 24 in each group will have 80% power to detect an effect size of 1.2 using a two-group t-test with a 0.05 two-sided significance level. For Aim3, baseline vs placebo/active M1 HD-tDCS, a sample size of 24 will have 80% power to detect an effect size of 0.8 using a paired t-test with a 0.05 two-sided significance level, allowing a wide range (0.1 to 1.0) of observable correlations within pairs.

Using the previous study, we approximated the SD as 20%/4 = 5% (range/4), and this gives us a detectable percentage change of 5*0.8=4 or higher.

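### Section 11.2's power statement for Aims 1 and 2 does not reproduce: as a standardised effect, 1.2 with 24 per group has 98% power, 80% power corresponds to about 0.83, and no other unit is defined

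*Combined protocol and SAP*

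**What the plan says.** Section 11.2 (Sample Size Considerations) allows for 20% dropout from 30 per group. For Aims 1 and 2 it states that "a sample size of 24 in each group will have 80% power to detect an effect size of 1.2 using a two-group t-test", at a two-sided significance level of 0.05. It gives no SD, raw difference or other unit for the 1.2.

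The next sentence covers Aim 3. It claims 80% power for an effect size of 0.8 with a paired t-test and n = 24, "allowing a wide range (0.1 to 1.0) of observable correlations within pairs". The section then takes an SD of 5% and multiplies it by 0.8 to get a detectable change of 4.

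The contrasts that the Aim 1 and 2 sentence has to cover are described elsewhere:

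- **Aim 1, baseline.** Section 3.3 (Primary Outcome Measures) and Section 11.1 compare baseline receptor binding in migraine patients with controls.
- **Aim 1, activation.** Section 3.3 expects that activation "during a sustained thermal pain threshold stress challenge will also be lower than in controls". Section 8.1.3 takes this from two phases of one scan, "10-40 min (baselines) and (3) 45-90 post tracer administration (pain or control".
- **Aim 2.** Active and sham stimulation are compared on clinical and experimental pain measures. In support, Section 11.1 cites a meta-analysis of non-invasive motor cortex stimulation in chronic pain that "indicated an effective size of -0.86 (95% C.I., -1.54, -0.19) on the VAS".

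**The concern.** The sentence gives everything needed for a two-group power calculation: group size, test, significance level, power and effect size. With four of these fixed, the fifth follows, so the sentence can be checked directly. An effect of 1.2 SD is very large for 24 per group, and one would expect power well above 80%.

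This is the only power statement for the Aim 1 and Aim 2 group comparisons, and Aim 1 carries the primary outcome. Anyone judging what a null result excludes would work from 1.2. A reader who set 1.2 beside the 0.86 cited for Aim 2 would conclude that the trial cannot detect the effect offered in its support.

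**Working it through.** **Inputs, all from Section 11.2:** 24 evaluable per group, two-group t-test, two-sided 0.05, effect size 1.2, stated power 80%. The dropout allowance is consistent: 24 / (1 − 0.20) = 30.

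**1. The plan's figure, standardised reading.** Power comes from the noncentral t with 24 + 24 − 2 = 46 degrees of freedom and noncentrality d × √(n/2).

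- At d = 1.2: 1.2 × √12 = 4.157, critical value 2.013, power **98.3%** (stated: 80%). A simulation of 200,000 trials gave 98.2%.
- Solving for 80% power: d = **0.826** (stated: 1.2).

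**2. Variants that might recover 80%.**

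| Variant | Power at 1.2 |
|---|---|
| One-sided 0.05, 24 per group | 99.3% |
| 30 per group (no dropout) | 99.5% |
| Both migraine arms pooled, 48 vs 24 | 99.7% |
| 1.2 as a raw difference with the section's SD of 5 (d = 1.2/5 = 0.24) | about 13% |
| 12 per group, 24 in total | 80.2% |

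Only the last row matches. It suggests that a total may have been reported as a per-group number, but that is inference, and the text says 24 in each group.

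**3. The unit hinted at by the Aim 3 sentence.** Let ρ be the within-person correlation. If effects are expressed in SDs of a single measurement, the SD of a change is √(2(1 − ρ)).

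For Aim 3 (paired, n = 24, effect 0.8):

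- At ρ = 0.1, 0.8/√1.8 = 0.596, and power is 79.9%, which matches the stated 80%.
- If 0.8 is in SDs of the difference, power is 96.3%.

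So the Aim 3 figure does reproduce on the raw-SD convention. Applying that convention to a between-group difference in change, 24 vs 24 (an assumption, since it is not stated for Aims 1 and 2), the detectable effect is 0.826 × √(2(1 − ρ)):

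| ρ | √(2(1 − ρ)) | 80% detectable effect | Power at 1.2 |
|---|---|---|---|
| 0 | 1.414 | 1.17 | 82.1% |
| 0.1 | 1.342 | 1.11 | 85.8% |
| 0.3 | 1.183 | 0.98 | 93.0% |
| 0.5 | 1.000 | 0.83 | 98.3% |

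The detectable effect rounds to 1.2 only for ρ below about 0.03. Over the 0.1 to 1.0 range given for Aim 3, power at 1.2 is at least 85.8%.

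**4. Which contrasts that unit could cover.** It could apply to Aim 1 activation, a change within one scan that is also measured in controls, and to Aim 2 changes from before to after treatment. It cannot apply to the baseline binding comparison, which has one value per person and so no within-person correlation. For that contrast the standardised figure of 0.83 is the relevant one.

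**5. The cited 0.86.** If it is a standardised effect (the protocol does not say so), the noncentrality is 0.86 × √12 = 2.979 and power with 24 per group is 83.1%.

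**The case against.** The best defence has three parts.

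First, 80% may be meant as a floor. The Aim 3 sentence claims 80% power over a whole range of correlations, where power cannot be constant, and the section calls the sample size conservative. On that view 98.3% satisfies the statement, and the sentence is loose but not false. This carries some weight, but the Aim 1 and 2 sentence gives no range, and a power statement of this form is ordinarily read as the detectable effect at that power.

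Second, the section never says that 1.2 is standardised, and the change-score reading at zero correlation gives 1.17, which rounds to 1.2. It is right that the unit is open, so the finding is conditional on the standardised reading. But the change-score unit is not stated for these aims, it needs a correlation below the lowest the section mentions, and it leaves out the baseline contrast. The section's own conversion for Aim 3 treats an effect size as a multiple of an SD.

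Third, the harm is limited. The 0.86 comes from chronic pain and is offered as reassurance, not as a design assumption, and its scale is not stated. That is correct, and the comparison with 0.86 is illustrative only.

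**Conclusion.** The concern holds. Taken as a standardised effect, the stated group size, power and effect size cannot all be right: 24 per group at two-sided 0.05 gives 98.3% power at 1.2, and 80% power corresponds to about 0.83. No unit stated in the plan reconciles them. The raw-SD change-score unit comes nearest but would need to be declared, together with its correlation, and could cover only some of the contrasts.

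The error is conservative. Enrolment is not too small for an effect of 1.2, and no test or decision rule is affected. It is a minor reporting error that understates the design's sensitivity. The arithmetic is secure. What the authors meant by 1.2 cannot be settled from the protocol.

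**What to change.** State the unit of the effect size in Section 11.2.

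- **If it is standardised**, replace the sentence with: 24 per group gives 80% power for a standardised effect of about 0.83 (98% for 1.2), two-group t-test, two-sided 0.05.
- **If 1.2 was meant in single-measurement SDs on change scores**, say so, give the assumed within-person correlation, and name the outcomes it covers. Add the separate standardised figure of 0.83 for the Aim 1 baseline binding comparison with controls.

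The cost is a rewording of one sentence. Enrolment, tests and decision rules stay as they are.

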11. STATISTICAL CONSIDERATIONS

The main contrasts of interest will be modeled using both volume-of-interest (VOI) data with SPSS and parametric statistical maps using the SPM8 package and a general linear model for the radiotracers. The main effect of interest [effect of acute and chronic pain, opioid and psychophysiological measures, before and after 10 M1 HD-tDCS sessions (active or sham) can be modeled by t-tests or ANOVA (e.g., effect of pain), or ANCOVA (with age as covariate), with post-hoc t-tests to determine the direction and magnitude of regional changes. However, a global model will also be utilized to determine the main effects of pain, and interactions with sex and other nuisance variables (e.g., age). In that manner, we will examine the main effects of migraine and repetitive M1 HD-tDCS neuromodulation on receptor BP_{ND}, BP_{ND} changes in the thalamus and other pain-related regions in response to an experimental pain challenge, interrelationships between variables, and additional interactions with covariates of interest and nuisance variables.

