Two sets of analyses will be completed with the PET data: Volume of Interest Analysis: First, we will conduct a hypothesis-driven VOI analysis in which selected brain areas are examined. It offers the advantage of a relatively narrow search within the thalamus and other regions already known to be involved in the regulation of pain and in sex differences in these phenomena (e.g., anterior cingulate, insular cortex, nucleus accumbens, amygdala, periaqueductal gray for [11C]carfentanil scans). Predefined VOIs obtained from the data acquired in previous studies (Zubieta et al., 2001; Scott et al., 2008) will be utilized for this purpose and applied to the functional image data in stereotactic space. The VOIs will then be transferred to the μ -opioid receptor BP_{ND} Statistical Parametric Mapping: In subsequent analyses, statistical parametric maps will be obtained using whole brain image subtraction routines utilizing the images warped to stereotactic coordinates, as above. SPM analyses will be employed for the radiotracer, as shown in the Preliminary Data. Differences between conditions and subject groups will then be mapped into stereotactic space using t-maps of statistical significance and SPM8 and Matlab software, using a general linear model and correction for multiple comparisons (Friston et al., 1995). These maps are displayed superimposed over the anatomically standardized T1-weighted MRI of the subjects. This second analysis does not assume that specific regions are involved selectively, and a brain-wide search is performed on a voxel-by-voxel basis. Only gray matter pixels and regions with specific binding are included in the statistical parametric analyses (voxels with BP_{ND} values > 0.2) (Wager et al., 2007). For each subtraction analysis, one- or two-sample t-statistic values are calculated for each pixel using a pooled smoothed variance across voxels (Worsley et al., 1992). Areas of significant differences are detected using a statistical threshold that controls a Type-I error rate at p = 0.05 for multiple comparisons, which is estimated using the Euler characteristic (Worsley et al., 1992) based on the number of pixels in the gray matter and image smoothness (Friston et al., 1991). We will also use a multiple comparisons procedure that controls the false discovery rate (FDR; (Genovese et al., 2002), particularly in the case of preliminary analyses (years 2-3) that would not be fully powered for standard multiple comparisons

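### Section 11.2 supports power only for single t-tests at uncorrected 0.05, yet Sections 11 and 11.1 imply that the family-wise corrected whole-brain maps are powered too

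*Combined protocol and SAP*

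**What the plan says.** Section 11.2 is the only sample-size calculation in the documents. For Aims 1 and 2 it says "a sample size of 24 in each group will have 80% power to detect an effect size of 1.2 using a two-group t-test". The level is 0.05, two-sided. For Aim 3 it says "a sample size of 24 will have 80% power to detect an effect size of 0.8 using a paired t-test", at the same level, for within-pair correlations from 0.1 to 1.0. Thirty per group are enrolled to allow for 20% dropout.

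Section 11 says: "The main contrasts of interest will be modeled using both volume-of-interest (VOI) data with SPSS and parametric statistical maps using the SPM8 package". The VOI analysis comes first and is hypothesis-driven. The map analysis follows and searches all gray matter with specific binding, voxel by voxel. Significance on the maps uses "a statistical threshold that controls a Type-I error rate at p = 0.05 for multiple comparisons", obtained from the Euler characteristic and described as family-wise control. An FDR procedure will be used as well, "particularly in the case of preliminary analyses (years 2-3) that would not be fully powered for standard multiple comparisons" correction.

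Section 11.1 (Aim 1, potential pitfalls) adds, while conceding that correlation tests have low power, that the study is powered for all its analyses. Section 11.6 leaves the final analysis plan to a SAP, which the Supplemental Materials list as a separately stored document.

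**The concern.** A test of one region mean at uncorrected two-sided 0.05 has a critical t of about 2.0. A whole-brain search at family-wise 0.05 needs a much higher value at each voxel. Power worked out for the first does not carry over to the second. Section 11 names only the year 2-3 analyses as short of power under correction, so a reader will take the final maps to be adequately powered, and Section 11.1 reinforces that.

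The maps are the only analysis that looks outside the predefined regions, and Objective 1 and the secondary BP_ND hypothesis reach beyond the thalamus. If the maps are believed to be fully powered, an empty map could be taken as good evidence that there is no mu-opioid difference, or no HD-tDCS effect, elsewhere in the brain.

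**Working it through.** **1. The plan's own figures.**
- Two groups of 24, d = 1.2, two-sided 0.05: noncentrality 1.2 × √(24/2) = 4.157; critical t (46 df) = 2.013; power = 98.3%, not 80%. With 24 per group, 80% power is reached at d = 0.83.
- Paired, n = 24, raw effect 0.8, correlation r = 0.1: dz = 0.8/√(2 × 0.9) = 0.596; power = 79.9%. This reproduces the printed 80% and shows that the formula is a single uncorrected paired test.
- Dropout: 24/(1 − 0.2) = 30, which agrees.
- Room for several VOIs: Bonferroni over the six regions named in Section 11 (0.05/6) leaves 91% for the two-group test at d = 1.2, but 52% for the paired test at r = 0.1.

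**2. Map threshold.** The documents give neither search volume nor final smoothness. Assumed: 400 to 1000 cm³, FWHM 6 to 12 mm, spherical search region. Resels R = volume/FWHM³, from 400000/12³ = 231 to 1000000/6³ = 4630. The threshold t solves expected Euler characteristic = 0.05. For a t-field with v degrees of freedom the leading term is

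R × (4 ln 2)^1.5/(2π)² × [((v − 1)/v)t² − 1] × (1 + t²/v)^(−(v − 1)/2),

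and the lower-dimensional terms are added. Section 11 plans a variance pooled over voxels, which is closer to a Gaussian field, so both cases were run.

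| Field | Threshold |
|---|---|
| t, 46 df (24 vs 24) | 4.93-5.95 |
| t, 70 df (48 vs 24) | 4.70-5.59 |
| t, 88 df (60 vs 30) | 4.61-5.46 |
| t, 23 df (paired, n = 24) | 5.76-7.32 |
| Gaussian | 4.31-5.00 |

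**3. Power at one affected voxel.** For the t-field, power = P(noncentral t > threshold). For the Gaussian case, power = Φ(noncentrality − threshold). The noncentrality is d√12 for 24 vs 24, d√16 for 48 vs 24, d√20 for 60 vs 30, and dz√24 for pairs, with dz = 0.8/√(2(1 − r)).

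| Contrast | t-field | Gaussian |
|---|---|---|
| 24 vs 24, d = 1.2 | 7-25% | 20-44% |
| Aim 1, 48 vs 24, d = 1.2 | 24-54% | 42-69% |
| Aim 1, 60 vs 30 (no dropout), d = 1.2 | 47-77% | 64-85% |
| Aim 3, raw effect 0.8, r = 0.1 | 0.1-2% | 2-8% |
| Aim 3, r = 0.5 | 1-9% | 14-35% |
| Aim 3, r = 0.8 | 24-65% | 88-97% |
| Aim 3, r = 0.9 | 85-99% | about 100% |

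Example, Gaussian, 24 vs 24: 4.157 − 4.31 = −0.15, so 44%; 4.157 − 5.00 = −0.84, so 20%.

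**4. Effect needed for 80% power at 24 vs 24.** Gaussian: (4.31 + 0.84)/√12 = 1.49 to (5.00 + 0.84)/√12 = 1.69. t-field: 1.69 to 1.99. Overall this is about 1.5 to 2.0.

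**The case against.** Sizing a trial on its hypothesis-driven test is ordinary practice, and the plan puts the VOI analysis first. That stands, and nothing here shows that the trial is too small for a thalamic VOI test. At d = 1.2 the two-group comparison has more power than claimed.

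A reader might infer that the protocol states outright that the final maps are fully powered. It does not: Section 11 says only that the year 2-3 analyses are not, and the rest is implication. The general statement in Section 11.1 makes the implication hard to avoid, but the separately stored SAP could contain a map-level calculation that is not in these documents.

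A reader might also infer that the maps will miss the planned effect in every contrast. They need not. Aim 1 with all 60 patients against 30 controls and pooled variance reaches 64-85%, and Aim 3 at a correlation of 0.9 reaches 85% or more. Power to find at least one peak in a broad affected region is higher than at a single voxel. FDR control is also planned, and not only for years 2-3. Its power depends on how much of the brain is affected, which the documents do not give, so it was not computed.

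The concern does not extend to Aim 2, which shares the two-group sentence but is judged on clinical and experimental pain measures. Nor does any section say that an empty map will be read as no effect. That is a risk of the current wording, not a stated intention.

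**Conclusion.** The concern holds as a mismatch between what Section 11.2 calculates and what Sections 11 and 11.1 imply. At 24 vs 24 and d = 1.2, map power stays well below 80% in both approximations over the whole assumed range. For Aim 1 with all migraine patients it is about 24-69% after the planned dropout, and 47-85% with none. For Aim 3 the claim fails at the low end of the stated correlation range (about 0.1-8% at 0.1), not everywhere. These sizes rest on the assumed 230 to 4630 resels, a spherical search region and a single affected voxel. They will move once the actual resel count and variance method are known. The 98% result for the printed two-group inputs needs none of these assumptions.

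**What to change.** 1. In Section 11.2, correct the two-group figure: 24 per group gives 98% power at d = 1.2, or 80% at d of about 0.83. For PET outcomes, say that the power figures apply to one test in one predefined VOI, the thalamus. Keep the corrected two-group statement for Aim 2, as a single test of a pain measure.
2. State there that the figures do not cover the family-wise corrected maps. Give the map-level detectable effect, about 1.5 to 2.0 at 24 per group for 80% power, to be updated with the actual resel count and variance method.
3. In Section 11, remove the implication that only the year 2-3 maps lack power under correction. In Section 11.1, remove the statement that all analyses are powered.
4. Label the maps, under family-wise or FDR control, as exploratory support for the VOI result, and say that a null map is not evidence of no effect elsewhere. Carry this into the SAP.

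The cost is wording and one short calculation, with no added patients, scans or procedures. The downside is a less favourable power statement for the maps.

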11.1. STUDY HYPOTHESES

How are endogenous µ-opioid mechanisms affected in migraine patients?

Aim 1. To demonstrate that clinical and experimental pain measures in migraine patients are associated with μ OR BP_{ND} in the thalamus and other pain-related regions, even during interictal phase (non-headache phase).

We hypothesize that migraine patients will have a reduction in μ OR BP_{ND} at the baseline level. The activation of μ OR neurotransmission, calculated as reduction in μ OR BP_{ND} during a sustained thermal pain threshold stress challenge, will also be lower than in controls and both these measures will be associated with clinical and experimental pain ratings.

Feasibility: (Aim1) During the K23 NIH-NINDS award period, we evaluated *in vivo* the μ -opioid system during spontaneous episodic migraine headaches. Seven patients were scanned at interictal and ictal phases using the selective μ -opioid receptor (μ OR) radiotracer [¹¹C]carfentanil (Figure 11). In the ictal phase there was dysfunctional μ OR activation in the medial prefrontal cortex (mPFC), an area highly related to clinical pain processing. Furthermore, μ -opioid binding changes in mPFC showed moderate negative correlation with the combined extension and severity of the attacks. These results indicated for the first time the acute activation of the endogenous μ -opioid neurotransmission interacting with μ OR due to the pain of the migraine attack (DaSilva et al., 2014a).

(Aim 1.2) When challenged for sustained thermal stimulus on the trigeminal ophthalmic region (STPTS) during the ictal and interictal phases, six of those migraineurs showed ictal allodynia that was concurrent and positively correlated with μ OR activation in the midbrain, extending from red nucleus to vIPAG. These findings demonstrate for the first time *in vivo* the high μ OR activation in the migraineurs' brains in response to their allodynic experience (Figure 12 & 13)(Nascimento et al., 2014b).

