Feasibility: (Aim 3.1) We conducted analysis to demonstrate that tDCS can significantly modulate μ-opioid mechanisms and trigeminal pain measures in vivo, even immediately. This is a unique advance in pain translation research in humans, previously only possible in animal models. We examined with PET nine healthy volunteers with no history of chronic pain or systemic disorders. The protocol consisted of two PET scans, using [11C]carfentanil, a selective µOR radiotracer (Figure 17). The first PET provided a baseline evaluation of regional µOR BPND. During the second PET, placebo and active (2mA) M1-SO tDCS sessions were delivered sequentially, 20 min each, the same M1-SO tDCS montage as in our proposed migraine study. When analyzed separately, placebo and active tDCS were both associated with an acute reduction in µOR BPND, indicating activation of this neurotransmitter system in the PAG. In addition, the initial sham tDCS phase induced immediate activation of µORs in the left thalamus (Thal) and post-cingulate cortex, (PCC) and subsequently during the active tDCS phase in the left pre-frontal cortex (PreF) and precuneus (PreC). However, only after active tDCS was there significant improvement of pain thresholds measured by quantitative sensory testing, which were correlated with µOR system activation (DosSantos et al., 2014b). Our results suggest that immediate global analgesia induced by the M1-SO tDCS application, sham and active, can be related to the recruitment of endogenous muopioid mechanisms.

Analysis: (Aim3) First, we will examine changes in baseline μ OR BPND and in the activation of μ -opioid neurotransmission between pre- and post- 10 active daily HD-tDCS treatments. A mixed model of variance, accounting for age and other potentially influencing variables (e.g., plasma levels of estradiol, testosterone) will be employed. Increases in baseline μ OR BPND and in the activation of μ -opioid neurotransmission from pre- to post- 10 HD-tDCS sessions in migraine will be expected, with an approximation towards control values. The Spearman nonparametric test will then be used to assess the correlation between the percentage of change pre- and post- 10 M1-tDCS sessions in the thalamus and each region where it was observed, and that of the acute and chronic pain relief.

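### The Aim 3 detectable change of 4% is not supported: range/4 fits none of the PET samples described, and the units of the SD that 0.8 multiplies are not stated

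*Combined protocol and SAP*

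**What the plan says.** Section 11.2 states for Aim 3 that "a sample size of 24 will have 80% power to detect an effect size of 0.8 using a paired t-test" at a two-sided 0.05 level, "allowing a wide range (0.1 to 1.0) of observable correlations within pairs". It then turns the effect size into binding-potential terms by reference to an unnamed previous study: "we approximated the SD as 20%/4 = 5% (range/4), and this gives us a detectable percentage change of 5*0.8=4 or higher".

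The section does not give that study's size, its endpoint or brain region. It also does not say whether the 20% is a spread of single scans between people or of changes within people.

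The PET samples described elsewhere are small:

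- Section 11.1, Aim 1 feasibility: "Seven patients were scanned at interictal and ictal phases". The allodynia result in the same section uses six of those seven.
- Section 11.1, Aim 3.1 feasibility: "We examined with PET nine healthy volunteers with no history of chronic pain or systemic disorders".
- Section 4: up to 10 previously scanned healthy controls, whose data will be reused.

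The Aim 3 analysis paragraph in Section 11.1 uses the percentage change from before to after the ten sessions.

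**The concern.** The 4% is the only statement of what size of change in µ-opioid receptor binding Aim 3 can detect. Two steps in its derivation look unsafe.

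The first is range/4. The expected range of a normal sample grows with its size, so a divisor of 4 suits one sample size, and that size is well above any PET sample described. With a smaller sample, range/4 tends to understate the SD.

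The second is the multiplier. For a paired test, an effect size may be expressed in SDs of a single measurement or in SDs of the within-person change. The two coincide only at a correlation of 0.5. Section 11.2 does not say which it uses, yet calls the product a percentage change.

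A reader of a null Aim 3 result may take the trial as able to exclude a 4% change. Whether it could depends on facts the plan omits.

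**Working it through.** **Inputs (Section 11.2).** 24 pairs, two-sided 0.05, 80% power, effect size 0.8, correlation 0.1 to 1.0, range 20%, SD 5%, detectable change 4%. PET sample sizes of 6, 7, 9 and 10 come from Sections 4 and 11.1.

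**1. Reproducing the stated power.** Let d_z be the mean change divided by the SD of change, and rho the within-pair correlation. If 0.8 is in single-scan SDs, d_z = 0.8/sqrt(2(1 − rho)). Power is from the noncentral t distribution with 23 degrees of freedom and noncentrality d_z × sqrt(24).

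- rho = 0.1: d_z = 0.8/sqrt(1.8) = 0.596; power 79.9%. This reproduces the stated 80%.
- rho = 0.5, or 0.8 read directly as d_z: d_z = 0.8; power 96.3%, and 15 pairs would be enough. This does not reproduce 80%.
- Exactly 80% power with 24 pairs needs d_z = 0.597.

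So 0.8 is a single-scan effect size at the lowest correlation named. The product 5 × 0.8 = 4 is correct arithmetic.

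**2. The upper correlation.** With equal variances, the SD of the difference is SD × sqrt(2(1 − rho)). At rho = 1.0 this is zero and no paired t-test exists. Within the range the detectable effect also varies. In single-scan SDs, 0.597 × sqrt(2(1 − rho)) is 0.80 at rho = 0.1, 0.60 at 0.5 and 0.27 at 0.9.

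**3. The range rule.** The expected range of n normal values, in SDs (d2), is 3.997 at n = 27. For the PET sample sizes, SD = 20%/d2:

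| n | d2 | SD | 0.597 × SD (range of changes) | 0.80 × SD (range of single scans, rho = 0.1) |
|---|---|---|---|---|
| 6 | 2.534 | 7.9% | 4.7% | 6.3% |
| 7 | 2.704 | 7.4% | 4.4% | 5.9% |
| 9 | 2.970 | 6.7% | 4.0% | 5.4% |
| 10 | 3.078 | 6.5% | 3.9% | 5.2% |

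At rho = 0.5, sqrt(2(1 − 0.5)) = 1, so single-scan SDs give the fourth column again: 3.9% to 4.7%.

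**4. Changing the multiplier alone.** If the 5% is correct and is an SD of change, the detectable change is 5 × 0.597 = 3.0%.

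**5. Power for a 4% change with 24 pairs.** It is 96% if the SD of change is 5%. With the SDs in the table it is 66%, 72%, 80% and 82% (n = 6, 7, 9, 10) if they are SDs of change, and 43%, 47%, 55% and 58% if they are single-scan SDs at rho = 0.1.

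**6. How firmly a small-sample range fixes the SD.** Simulation of normal samples with an observed range of 20% gives 95% limits for the SD of 4.3% to 12.9% at n = 9 and 4.6% to 18.7% at n = 6. An SD of 5% is therefore on the low side but not excluded.

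**The case against.** The best defence is that the plan can be read consistently. If the 20% is a range of single-scan values expressed as a percentage of the mean, 0.8 is the matching multiplier and 4% is in the right units. The correlation of 0.1 is then a conservative floor, because any higher value gives more power. If the 20% describes a population spread covering about 95% of people, range/4 is an accepted planning approximation whatever the sample size. The source might not be one of the small PET studies: Section 11.1 also describes a 24-patient HD-tDCS trial, for which d2 is 3.895 and the SD 5.1%. Finally, the 4% sets nothing. The 24 pairs come from the effect size of 0.8, and the 30 per group from 20% dropout.

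Much of this stands. A reader might infer that 0.8 is simply the wrong multiplier; Section 11.2 never says that the range is of within-person changes, so that is conditional. A reader might also infer that 4% is too small and that the trial is clearly underpowered for it. The documents do not support that either. With nine subjects and a range of changes, the understated SD and the overlarge multiplier nearly cancel and return 4.0% with 80% power. The 5.2% to 6.3% figures need single-scan data and a correlation of 0.1, and nothing in the documents says that repeat scans would correlate so weakly.

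What does not stand is the 24-patient trial as a source. As described, it reports pain, mouth-opening and mood outcomes and no receptor binding. Nor does agreement at 4.0% under one set of assumptions justify the rule used to reach it.

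**Conclusion.** The derivation of the 4% is unsupported; the figure itself is not shown to be wrong in either direction. Depending on what Section 11.2 leaves out, the detectable change is 3.0% (only the multiplier wrong), about 3.9% to 4.7% (a range of changes, or of single scans at correlation 0.5), or 5.2% to 6.3% (single scans at correlation 0.1). Including a correlation of 1.0 is an error on any interpretation.

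The 3.9% to 6.3% figures assume normal data and that the 20% is an observed range from one of the PET samples of 6 to 10 subjects. The single-scan figures also assume equal variances. If the 20% is a population spread, the objection to range/4 falls away and only the units and the correlation remain to be settled. Severity is low, since no sample size or decision rule uses the 4%. Confidence is moderate, since the source is not named.

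**What to change.** In Section 11.2, name the previous PET study and its sample size, and say what the 20% measures. Replace range/4 by the SD of the individual percentage changes computed from that study's data, and state the detectable change as 0.60 × that SD for 24 pairs. If only a single-scan SD is available, use SD × 0.60 × sqrt(2(1 − rho)) at one stated correlation. If only the range is available, divide it by the factor for that study's n (2.53, 2.70, 2.97 or 3.08 for 6, 7, 9 or 10 subjects). Delete the correlation range of 0.1 to 1.0.

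The cost is one restated paragraph and a figure that may move up or down. No extra patients are needed.
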